#### 7.3. **Premature Withdrawal from the Study**

A patient has the right to withdraw from the study at any time, for any reason, and without repercussion.

The investigator and/or sponsor have the right to withdraw a patient from the study if it is no longer in the interest of the patient to continue in the study, or if the patient's continuation in the study places the scientific outcome of the study at risk (eg, if a patient does not or cannot follow study procedures). An excessive rate of withdrawals would render the study uninterpretable; therefore, unnecessary withdrawal of patients should be avoided.

Patients who are withdrawn prematurely from the study will be asked to complete the early termination visit, as described in Section 9.1.2.

Rules for discontinuation of study treatment (permanent or temporary) are discussed in Section 8.4.2.

REGENERON CONFIDENTIAL Page 46 of 99

# 7.4. Replacement of Patients

Patients prematurely discontinued from study/study drug will not be replaced.

REGENERON CONFIDENTIAL

Page 47 of 99

VV-RIM-00295189-1.0 Approved - 24 Mar 2023 GMT-5:00

### 8. STUDY TREATMENTS

#### 8.1. Investigational and Reference Treatments

Dupilumab drug product is supplied for this study in the following concentration:

- Dupilumab 150 mg/mL: Each 2.0 mL single-use prefilled glass syringe with snap-off cap delivers 300 mg of study drug (2.0 mL of a 150 mg/mL solution)
- Placebo-matching dupilumab is prepared in the same formulation without the addition of protein (ie active substance, anti-IL-4R $\alpha$  monoclonal Ab).

Study drug will be administered by SC injections. Subcutaneous injection sites of study drug should be alternated among the different quadrants of the abdomen (avoiding navel and waist areas), upper thighs, and upper arms so that the same site is not injected for 2 consecutive administrations.

Dupilumab will be administered as a 600 mg loading dose on day 1, followed by 300 mg administered SC Q2W.

Matching placebo will be administered SC Q2W.

Instructions on dose preparation are provided in the pharmacy manual.

#### 8.2. Background Treatments

Prior to screening, patients must be on a stable background therapy for asthma for at least 3 months with a stable dose  $\geq 1$  month, and all background therapy must remain stable between screening and baseline. Asthma controller medications must include ICS and may include 1 or more additional controller medications (eg, LABA, LTRA, LAMA). Patients requiring a third controller are allowed to participate in this study. The third controller should also be used for at least 3 months with a stable dose  $\geq 1$  month prior to screening and between screening and baseline.

Patients requiring systemic corticosteroids (prednisone or equivalent) up to 10 mg per day, or up to 30 mg every other day, for ABPA are also permitted. Oral corticosteroid doses will be down-titrated starting 4 weeks after randomization according to the schedule described in Appendix A.

Patients receiving oral antifungal therapy at baseline are permitted to enroll. For patients receiving antifungal therapy during the 24- to 52-week treatment period, the dose and regimen should remain stable until the end of the treatment period. However, antifungal discontinuation or modification to the dose or regimen is permitted for the following reasons: side effects, intolerance, or lack of efficacy (eg, acute exacerbation) as determined by the investigator.

Patients will be required to continue all background asthma controller medications (ICS) with or without long-acting beta agonist (LABA), leukotriene receptor antagonist (LTRA), or long-acting muscarinic receptor antagonist (LAMA) without any changes in the dose or regimen during the study period. However, if 2 or more exacerbations occur during the treatment period, changes to background therapy (eg, changes to background asthma controller medication or initiation of antifungal therapy) may be made at the investigator's discretion.

#### 8.3. Rescue Treatments

Short-acting bronchodilators (SABA) are permitted as rescue therapy throughout the study. Rescue therapy with ICS and/or LABAs is not permitted.

Systemic corticosteroids are allowed as rescue treatment for exacerbation. The need for rescue therapy and dosage will be determined by the site investigator. For patients on chronic systemic corticosteroids, an increase in the dose of systemic steroids is allowed as rescue treatment.

If 2 or more exacerbations occur during the treatment period, antifungal therapy may be initiated (or the dose may be increased for patients on antifungal therapy) after consultation with the medical monitor at the discretion of the investigator.

Patients receiving rescue therapy permitted by the protocol may continue to receive study drug. They will remain blinded and will be asked to return to the clinic for all remaining study visits for the double-blind treatment period and the follow-up period, and participate in all assessments for these visits according to the Schedule of Events specified in Table 1.

#### 8.4. Dose Modification and Study Treatment Discontinuation Rules

#### 8.4.1. Dose Modification

Study drug dose modification for an individual patient is not allowed.

#### 8.4.2. Study Drug Discontinuation

Patients who permanently discontinue from study drug should be encouraged to remain in the study. Those who agree and do not withdraw from the study will be asked to return to the clinic for all remaining study visits per the visit schedule.

Patients who permanently discontinue from study drug and who opt to withdraw from the study will be asked to complete study assessments, per Section 9.1.2.

#### 8.4.2.1. Reasons for Permanent Discontinuation of Study Drug

Study drug dosing will be permanently stopped in the event of:

- Evidence of pregnancy
- Serious or severe allergic reactions considered related to study drug
- Specific types of liver dysfunction (eg, Hy's law is met ([Guidance for Industry Drug Induced Liver Injury: Premarketing Clinical Evaluation FDA 2009])
- Patient withdraws consent
- If, in the investigator's opinion, continuation in the study would be detrimental to the patient's well-being
- In the event of a critical protocol deviation, at the discretion of the investigator or the sponsor
- At the specific request of the sponsor

REGENERON CONFIDENTIAL Page 49 of 99

- Diagnosis of a malignancy during study, excluding carcinoma in situ of the cervix, or squamous or basal cell carcinoma of the skin. Patient must be withdrawn for these latter malignancies if they cannot be adequately treated by local resection.
- Any opportunistic infection or other infection whose nature or course may suggest an immunocompromised status
- Severe laboratory abnormalities assessed as related to study drug:
  - Neutrophil count  $\leq 0.5 \times 10^3/\mu L$
  - Platelet count  $\leq 50 \times 10^{3}/\mu L$
  - ALT and/or AST values >3  $\times$  ULN with total bilirubin >2  $\times$  ULN, excluding confirmed Gilbert's Syndrome
  - Confirmed AST and/or ALT  $>5 \times$  ULN (for more than 2 weeks)

Any abnormal laboratory value or ECG parameter will be immediately rechecked for confirmation before making a decision of permanent discontinuation of study drug for the concerned patient. See Table 1 for information on follow-up and any further evaluations that need to be completed.

#### 8.4.2.2. Reasons for Temporary Discontinuation of Study Drug

Study drug dosing may be temporarily discontinued in the event of:

- Severe laboratory abnormalities (as noted in Section 8.4.2.1) where a causal relationship to study drug can be reasonably excluded, (ie, an alternative cause is evident): study drug will be discontinued but may be resumed when the laboratory abnormality is sufficiently normalized. At minimum, the laboratory value(s) must return to a level that no longer meets the specified criteria for discontinuation, as defined in Section 8.4.2.1. A decision to resume study treatment will be made jointly by the investigator and medical monitor.
- Infections or infestations that do not respond to medical treatment
- Other intercurrent illness or adverse event or major surgery which could, in the opinion of the investigator, present an unreasonable risk to the patient as a result of his/her continued use of the study drug

After the condition leading to temporary discontinuation of study drug resolves, study drug dosing may resume. A decision to temporarily discontinue study drug and/or resume study drug dosing should be discussed with the Regeneron Pharmaceuticals, Inc. medical monitor. Re-initiation of treatment with the study drug will be done under close and appropriate clinical and/or laboratory monitoring once the investigator will have considered, according to his/her best medical judgment, that the AE is sufficiently resolved and unlikely to recur after resuming therapy with the study drug.

The investigator may temporarily discontinue study drug dosing at any time, even without consultation with the medical monitor if the urgency of the situation requires immediate action and if this is determined to be in the patient's best interest. However, the Regeneron medical

monitor should be contacted as soon as possible. Resumption of study drug dosing requires consultation and agreement between the investigator and the Regeneron medical monitor.

For visits other than the randomization and EOT visits, if a patient is unable to return to the clinic for a given visit within the specified visit window, any follow-up procedures scheduled for the missed visit should be performed at the subsequent visit.

If the patient misses more than 4 consecutive doses, the patient will be permanently discontinued from the study.

For all temporary discontinuations of study intervention, duration must be recorded by the investigator in the electronic case report form (eCRF). Following a temporary interruption or missed dose, the investigational medicinal product (IMP) treatment should be reinitiated at the next scheduled visit, maintaining the original dose.

If a patient requires a prohibited medication at any time during the study, the investigator should contact the Regeneron medical monitor (except for illness requiring prompt treatment). Based on the discussions, study drug may be continued or temporarily or permanently discontinued.

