#### Patients on Chronic Oral Corticosteroids at Baseline:

REGENERON CONFIDENTIAL

Page 36 of 99

Patients who experience a severe respiratory exacerbation will have, as soon as possible, an unscheduled visit at the site for the collection of a blood sample for serum total IgE measurement.

Patients who withdraw from the study prematurely will have, at the time of their next regularly scheduled visit, an early termination visit. This early termination visit will consist of all assessments normally planned for the end of study (EOS) visit. To allow assessment of patient outcomes over the stipulated study period, patients who discontinue study treatment but continue in the study will be asked and encouraged to complete all remaining study visits and participate in all safety follow-up assessments according to the visit schedule (Table 1).

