#### 9.1.1. Footnotes for the Schedule of Events Table

#### Footnotes for Table 1 Schedule of Events

\*Visits 5, 7, 9, and 10 will be performed as phone visits for patients not receiving OCS at baseline. For patients receiving OCS at baseline, these visits should be performed in-clinic if the patient remains on OCS on the day of the clinic visit. If OCS has been discontinued, these visits can be either in-clinic or performed as a phone visit at the discretion of the investigator. Assessments/procedures marked with an asterisk should only be performed if the visit occurs in-clinic.

\*\*After the last patient has completed visit 14/week 24 of the treatment period or withdrawn from the study, all patients still currently in the treatment period (between visit 15/week 26 and visit 27/week 50) should return to the clinic 2 weeks from their last dose/treatment administration to complete their EOT visit and all its applicable assessments. For patients who have withdrawn from the study treatment but remain in the study, the EOT visit will take place 2 weeks from their last visit. All patients must have their EOS visit 12 weeks after their EOT visit.

- a. Prior to screening, patients must be on a stable background therapy for asthma which may include ICS in combination with a second controller medication (eg, LABA, LTRA, theophylline, etc) for at least 3 months with a stable dose ≥1 month prior to baseline. Patients requiring a third controller are allowed to participate in this study. The third controller should also be used for at least 3 months with a stable dose ≥1 month prior to visit 1. Patients requiring systemic steroids of up to 10 mg per day (or up to 30 mg every alternate day) as controller medication are permitted.
- b. Randomization/baseline visit is defined as day 1. The visit schedule should be adhered to within  $\pm 1$  week for the screening period,  $\pm 3$  days for the randomized IMP treatment period, and  $\pm 7$  days for the post-IMP treatment period.
- c. All assessments at visit 2 (day 1) are to be conducted pre-IMP dose except for the assessment of local tolerability of SC injections.

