#### 9.1.2. Early Termination Visit

Patients who are withdrawn from the study will be asked to return to the clinic once at the time of the next regularly scheduled visit for an early termination visit consisting of the end of study assessments described in Table 1.

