#### 9.1.4. End of Treatment Visit

After the last patient has completed visit 14/week 24 of the treatment period or withdrawn from the study, all patients still currently in the treatment period (between visit 15/week 26 and visit 27/week 50) should return to the clinic 2 weeks from their last dose/treatment administration to complete an EOT visit consisting of the assessments described in Table 1. For patients who have withdrawn from the study drug but remain in the study, the EOT visit will take place 2 weeks from their last visit.

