Change from baseline in pre-bronchodilator FEV1 at week 24	
 
strategies
 
The intercurrent events will be handled using the treatment policy strategy as follows: 
 
Taking rescue medications with systemic corticosteroids and/or oral antifungal drugs (including an increase in dose) for asthma or ABPA for any reason: all endpoint data collected after use of rescue medication will be used in the analysis
 
Taking prohibited medications: all endpoint data will be included in the analysis irrespective of use of prohibited medications
 
Discontinuing the study treatment: all endpoint data collected after discontinuation will be used in the analysis
 
 
 
	approaches Two types of missing data: 1) Patients discontinuing from the study prior to the analysis time point (week 24) will have missing data from the time of discontinuation through week 24; 2) Some intermittently missing data are expected because of occasionally missing a study visit while continuing with the randomized treatment Missing data handling: for both types of missing data, the primary analysis MMRM model assumes that missing data are MAR, that is, that patients with missing data would have efficacy outcomes like those in similar patients in their treatment group who continue their randomized treatment through the time point at which data are	
	anary 515	randomized treatment through the time point at which data are missing	

For the primary estimand of interest for the primary endpoint, the intercurrent events, strategies, and the corresponding missing data handling approaches are provided as below:

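### Protocol 8.4.2.2 removes patients from the study, not only from study drug, after more than four consecutive missed doses, and so can cut off off-drug data that the primary estimand uses

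*Protocol*

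**What the plan says.** Protocol 8.4.2.2, on temporary discontinuation of study drug, contains this rule: "If the patient misses more than 4 consecutive doses, the patient will be permanently discontinued from the study". It is mandatory, has no exception, and no reason is given beside it.

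Other parts of the plan point the other way:

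- Protocol 8.4.2, the parent section: "Patients who permanently discontinue from study drug should be encouraged to remain in the study". Those who agree are asked back for all remaining visits.
- Protocol 6.1: "patients who discontinue study treatment but continue in the study will be asked and encouraged to complete all remaining study visits".
- Protocol 7.3: "unnecessary withdrawal of patients should be avoided". The same section also lets the investigator or sponsor withdraw a patient whose continuation puts the scientific outcome at risk.
- Protocol 9.1.4 times an end-of-treatment (EOT) visit "For patients who have withdrawn from the study drug but remain in the study".
- SAP 5.2 says that off-drug patients may stay in the study, and it counts treatment-period completers who stopped drug early.
- The estimand table in Protocol 11.4.3: "Discontinuing the study treatment: all endpoint data collected after discontinuation will be used in the analysis". SAP 7.2.1.1 says the same, through Week 24.
- SAP 7.2.2 counts off-drug severe exacerbations up to the EOT visit, or to last contact if there is no EOT visit.

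Under Protocol 9.1.2, withdrawn patients "will be asked to return to the clinic once at the time of the next regularly scheduled visit" for the end-of-study assessments, which include spirometry.

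**The concern.** A site cannot both remove a patient from the study and encourage that patient to stay. The patients caught have been without drug for at least ten weeks. They supply exactly the off-drug observations that a treatment-policy analysis is meant to use.

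Where Week 24 FEV1 goes missing, the mixed model predicts it under a missing-at-random assumption. Protocol 11.4.3 describes that assumption as outcomes like those of similar patients in the arm who continue randomized treatment. A value that could have been observed off drug is then replaced by a model prediction or, for some last-dose weeks, by an earlier value. The estimand strategy itself does not change. What suffers is the data behind it.

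**Working it through.** **Plan's own figure.** The only related figure is the power of about 96% (Protocol 11.2). Its SD, difference and dropout rate are redacted, so it cannot be reproduced, and this point does not dispute it. For context, with assumed dropout of 0 to 20%, 96% power implies a difference/SD of about 0.97 to 1.09 (two-sample t-test). Losing 1, 2 or 3 further patients per arm would leave about 95%, 94 to 95%, or 93 to 94%.

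**Inputs.**
- Dosing every 2 weeks from Week 0 (Protocol 8.1).
- Removal at the fifth consecutive miss (8.4.2.2).
- One early termination (ET) visit (9.1.2).
- Study day = 7 × week + 1.
- Week 24 spirometry window, Days 121 to 197 (SAP Table 3).
- In-clinic visits for everyone at Weeks 2, 4, 8, 12, 24, 36 and 44. Weeks 18, 20 and 22 are phone visits for everyone. For Weeks 6, 10, 14 and 16 the footnote says: "Visits 5, 7, 9, and 10 will be performed as phone visits for patients not receiving OCS at baseline". Patients still on oral corticosteroids (OCS) attend those visits in clinic.

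**Timing.** With the last dose at Week L, the fifth miss is at Week L + 10. Protocol 9.1.2 does not settle what happens when the next scheduled visit is a phone visit, so there are two readings:
- A: ET visit in clinic at the next scheduled visit, Week L + 12, Day 7(L + 12) + 1.
- B: ET visit at the next visit planned as in-clinic after Week L + 10.

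| Last dose (week) | A: ET week (day) | A: Week 24 FEV1 | B: Week 24 FEV1 |
|---|---|---|---|
| 0 | 12 (85) | missing | missing (ET at Week 12) |
| 2 | 14 (99) | missing | observed; missing if OCS patient seen at Week 14 |
| 4 | 16 (113) | missing | observed; missing if OCS patient seen at Week 16 |
| 6 | 18 (127) | mapped, 6 weeks early | observed |
| 8 | 20 (141) | mapped, 4 weeks early | observed |
| 10 | 22 (155) | mapped, 2 weeks early | observed |
| 12 | 24 (169) | observed | observed |

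A shift of ±3 days changes no cell. From a last dose at Week 14, the fifth miss falls at Week 24 or later and the primary endpoint is untouched.

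**Permanent stoppers caught on the literal reading.** A 52-week patient has 26 planned doses (Weeks 0 to 50), so five or more remain if L ≤ 40. A 24-week patient has 12 (Weeks 0 to 22), so five or more remain if L ≤ 12.

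**Exacerbation follow-up lost under A.** For planned treatment of T weeks, the loss is T − (L + 12) weeks. At T = 52 it is 40 for L = 0, 28 for L = 12 and 0 for L = 40. At T = 24 it is 12 for L = 0, 2 for L = 10 and 0 for L = 12. The offset in SAP 7.2.2 ends at last contact, so it shortens with the follow-up.

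**Ceiling on the primary estimate.** Take the 0.26 L post-hoc subgroup difference in Protocol 3.3.1 and assume 30 patients per arm. Assume also that the whole effect is lost off drug, and that the model ignores the patient's own earlier values. Each dupilumab patient with Week 24 missing then moves the arm mean by at most 0.26/30 = 0.0087 L. For an assumed 1, 2 or 3 such patients the ceiling is 0.009, 0.017 or 0.026 L.

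**The case against.** The strongest reply is that the rule concerns temporary interruptions only. It sits under that heading, and a following paragraph speaks of a missed dose for a patient who will restart. Compliance (Protocol 11.4.5.4) counts planned injections only within the exposure period, and exposure (11.4.5.3) runs to 14 days after the last dose. On that usage a permanent stopper has no further doses to miss and stays under 8.4.2. This is a fair reading. A reader might infer that the sentence defeats 8.4.2 outright, or empties the SAP 5.2 row for early stoppers of all but those with one to four doses left. That follows only from the literal reading, and the documents do not settle which reading applies. The narrower reading still removes patients after a long interruption, and the estimand makes no exception for them.

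The wording of 6.1 and 9.1.4 is conditional on the patient remaining, and SAP 5.2 only gives permission. Those clash in intent; the direct conflict is with 8.4.2. Protocol 7.3 contemplates withdrawing patients who do not or cannot follow procedures, so removal for missed doses may be deliberate. But 7.3 grants a discretion, whereas 8.4.2.2 is automatic.

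The plan also absorbs part of the damage. FEV1 collected before removal stays in the model, study withdrawal is an anticipated type of missing data, and a tipping point analysis follows if the primary result is significant. None of these replaces a value that could have been observed.

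**Conclusion.** The conflict between 8.4.2.2 and 8.4.2 is real and nothing in either document reconciles it. It may be a slip for study drug, but the wording is current and sites must follow it. It is worth correcting because the correction is nearly free, not because the effect is large.

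One might infer that every last dose at Week 10 or earlier costs the Week 24 value. The documents do not support that. Last doses at Weeks 6 to 10 yield either a mapped earlier value or a true Week 24 value, provided the ET visit is attended. The slot is empty only for last doses at Week 4 or earlier under reading A, and for fewer patients under B. Nor do they support a claim that the estimand changes, that the power figure is wrong, or that exacerbation rates have a wrong denominator. Those rates are secondary and no longer compared with placebo, so the loss there is precision within each arm.

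The number of patients affected is unknown and may be none. The ceiling of about 0.009 L per affected dupilumab patient rests on the four assumptions listed with it: the 0.26 L subgroup difference, 30 patients per arm, full loss of effect off drug, and no use of the patient's own data.

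**What to change.** In Protocol 8.4.2.2, have the patient discontinued *from study drug* rather than *from the study*. Add that follow-up under 8.4.2, including spirometry through Week 24, continues unless the patient withdraws. The dosing rule stays as it is. The cost is a few words and one sentence in an amendment or clarification letter, and the visits are already in the schedule.

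If follow-up is already complete, which is plausible because SAP 14.3 describes enrolment in the past tense, report the consequence instead. In the SAP 5.2 disposition output, give by arm the number removed under this rule, their last-dose week, and whether Week 24 FEV1 was observed, mapped from the ET visit, or missing. If a listing is preferred, name it as one required for the clinical study report, because SAP 1.4 limits listings to those. Either way the cost is a few extra rows or columns in planned output.
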